## 1. Research Background

Elderly patients have reduced organ function, often with comorbidity, and the incidence of complications and mortality are significantly higher after undergoing anesthesia and surgical trauma than those in other adult patients.[1-3] At the same time, elderly patients often have problems with hemodynamic instability such as hypotension during the induction of anesthesia.[4]

Eomidate, a widely used general anesthetic, is often used for induction of general anesthesia in elderly or hemodynamically unstable patients because of its small effects on blood pressure and heart rate. However, etomidate has an inhibitory effect on adrenal function and can cause muscle tremor and stiffness. Moreover, some studies have shown that etomidate anesthesia increases postoperative nausea and vomiting (PONV), which may not be conducive to patient prognosis and reduce satisfaction.[5]

Remazolam (RT) is a new ultra-short-acting benzodiazepine drug that has been approved for clinical use since 2019. It is characterized by rapid hydrolysis into inactive carboxylate metabolites by ubiquitous tissue esterases. Compared to the classic benzodiazepine midazolam.[6-8] Also, like the other benzodiazepines, remazolam can be antagonized by the flumazenil injection. A recent study showed that remazolam is more stable hemodynamic than propofol during anesthesia.[9]

With significant advances in surgical techniques, the proportion of patients undergoing day surgery with postoperative

complications has gradually decreased. Current perioperative care that improves the recovery of surgical patients focuses more on the time to restore normal function and the subjective postoperative experience, rather than just the incidence of complications. The Quality of Recovery (QOR) score, as an objective measure of patient-centered surgery and post-anesthesia general health, is often used to assess the quality of postoperative recovery, where QoR-15 is a reliable tool for assessing early postoperative recovery [10] and has been validated for [12] in patients undergoing various surgical procedures.

If hemodynamic stabilization during the etomidate induction phase can be achieved with another anesthetic without the above associated side effects, and the quality of postoperative recovery is no worse than that in elderly patients receiving etomidate, this would provide a new option for the induction of anesthesia during daytime surgery in elderly patients. In this study, we aimed to evaluate the quality of recovery following general anesthesia with remazolam-induced laryngeal mask in elderly day surgery patients, comparing that of remazolam versus etomidate, to better guide anesthesiologists in the choice of intraoperative induced medication in elderly patients.

## **Effect of general anesthesia on the quality of recovery after day surgery in elderly patients: a comparative study with etomidate induction**

### **1. Purpose Of Research**

**To compare the quality of postoperative recovery induced by general anesthesia with Remimazolam and etomidate in elderly patients undergoing day surgery.**

### **2. Study Design And Methods**

#### **1. Research Design**

##### **1.1 Study Objectives**

The study plans to use the Chinese version of QoR-15 score to evaluate the quality of postoperative recovery after general anesthesia in elderly day surgery patients receiving remazolam or etomidate, while observing hemodynamic changes and other adverse effects.

##### **1.2 Study Content**

This study is a randomized, double-blind parallel-controlled non-inferiority trial to enroll 112 elderly day surgery patients randomized at 1:1 to receive Remazolam or etomidate-induced general anesthesia after inclusion 1, along with three QoR-15 assessments to assess the quality of their recovery after surgery.

##### **1.3 Primary outcome measures: quality of recovery at 24h after surgery (QoR-15 score)**

Secondary study index: time of eyelash reflex disappearance after induction; SpO2, HR, MBP, and frequency of use of vasoactive drugs during anesthesia; incidence of adverse events in PACU.

#### 1.4 Subject selection

Selection criteria:

- 1) Age:> 65 years old and above;
- 2) The American Association of Anesthesiologists (ASA) is grades I-III;
- 3) The body mass index (body mass index) was 18-30 kg/m^2;
- 4) Voluntary provide written informed consent;
- 5) The patient underwent day surgery under general anesthesia with a laryngeal mask.

Exclusion criteria:

- 1) Cognitive dysfunction and neuropsychiatric disorders;
- 2) Use of benzodiazepines or opioids within 1 month;
- 3) Patients with contraindications or allergies to benzodiazepines, opioids, etomidates and their components;
- 4) Patients estimated to have a difficult airway;
- 5) Have adrenocortical insufficiency, porphyria, or have received chronic corticoid therapy.

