### 2. Research methods

2.1 Study design: Randomized, controlled, parallel non-inferiority trial

Randomization: The randomization result was generated by the investigator using R software, sealed to the envelope and handed over by the patient to the anesthesia nurse before surgery, who was responsible for unpacking the randomized envelope.

Blinding: The anesthesia nurse was responsible for unpacking the randomized envelope and preparing drugs to cover the syringes (with the same appearance and volume), and blinded the anesthesiologist, postoperative visitors and patients.

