## **3. Observation Items And Monitoring Time Point**

### **1. 1. Baseline metrics**

The following data were collected during the patient screening period

Demographic data: age (yr), gender, education level, ASA grade, body mass index, diagnosis and preoperative comorbidities, and history of smoking and alcohol abuse.

Preoperative clinical data: pulse oxygen saturation (SpO2), Non-invasive blood pressure (NIBP), heart rate and other vital signs, and electrocardiogram.

The following data will be collected during the surgical treatment period:

SpO2, HR, systolic blood pressure, diastolic blood pressure, MBP, test time points including 5 minutes before induction of anesthesia, 1 minute after induction, 1 minute after laryngeal mask placement, and start of surgery. Where, data recorded 5 min before induction of anesthesia served as baseline.

The following data were collected during the PACU recovery period:

SpO2, HR, systolic BP, diastolic BP, and MBP

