## **4. Efficacy Evaluation Criteria**

### **1. Main outcome measures:**

The primary outcome measure was the quality of recovery at 24h after surgery (QoR-15 score), recording the QoR-15 score 1 day before surgery, 1 day after surgery (POD 1) and 2 days after surgery (POD 2). The POD 1 score was the primary study outcome.

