## 2. Statistical analysis method

Data management was performed by EpiData software; SPSS26.0 software was used for statistical analysis. Quantitative variables were tested for normality by using the Shapiro - Wilk test. Comparison of quantitative variables with normal distribution between groups were performed by the t-test, and quantitative data with asymmetric distribution were analyzed by the Mann Whitney U-test. Qualitative variables were compared between groups with the chi-square test or Fisher's exact test as needed. Data for the QoR-15 score are also expressed as the median difference and their 95% confidence interval (CI). Median difference is the median of all pairwise differences between the two sets of observed values, with the 95% CI estimated by Hodges-Lehmann. Data on the frequency of adverse events were reported by the proportion difference and their 95% CI. The 95% CI of proportional differences was calculated using the Wilson program. Among other parameters, such as patient demographic parameters, SpO2, HR, MBP, and vasoactive drug application frequency, median or proportional differences and their 95% CI were calculated as described above. All analyses were assessed using two-sided tests and a P-value less than 0.05 was considered statistically significant.

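### Any laryngeal-mask day operation is eligible, yet no stratification is described and the POD 1 QoR-15 comparison is unadjusted, so variation between operations stays in the error term and precision is lost

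*Combined protocol and SAP*

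**What the plan says.** **Eligibility.** Section 1.4, selection criterion 5, reads "The patient underwent day surgery under general anesthesia with a laryngeal mask". No specialty, procedure or duration is named, and none of the five exclusion criteria restricts the operation.

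**Allocation.** Section 1.2 gives "112 elderly day surgery patients randomized at 1:1". Section 2.1 adds that "The randomization result was generated by the investigator using R software" and was sealed in envelopes. It mentions no strata, blocks or minimisation factors.

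**Endpoint.** Section 4, item 1: "The POD 1 score was the primary study outcome". The item table in section 3 includes moderate and acute pain, nausea and vomiting, personal hygiene, and taking part in work or daily activities.

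**Analysis.** In section 5, item 2, "Comparison of quantitative variables with normal distribution between groups were performed by the t-test", while "quantitative data with asymmetric distribution were analyzed by the Mann Whitney U-test". QoR-15 is also reported as a Hodges-Lehmann difference: "Median difference is the median of all pairwise differences between the two sets of observed values". No covariate or stratified analysis is planned.

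**Data collected.** The baseline list in section 3 has "diagnosis and preoperative comorbidities". Type of operation is not listed.

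**The concern.** One day after surgery, pain, nausea, self-care and return to daily activity plausibly differ between operations, whatever the induction drug. The trial mixes operations without limit, and neither the described allocation nor the planned analysis takes account of the mix. The preoperative QoR-15 cannot stand in for it, because it is scored before the operation.

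Two things follow. The confidence interval set against -8 is wider than it would be if the category of operation were recorded and used. And if one arm happens to receive more of the operations with poorer early recovery, the realised estimate moves by that amount. Adding an adjustment only after seeing such an imbalance would be a post hoc choice, so it is better specified now.

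**Working it through.** **Inputs from the sample size section (2.2).** Margin -8 on the mean difference; SD 14; 56 per group; 10% dropout; type 1 error 0.05, sidedness not stated; power 90%. Scored per arm: 56 × 0.9 = 50.4, taken as 50.

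**Assumption.** The documents do not give the share of POD 1 QoR-15 variance due to operation (R²). I use 0, 5%, 10% and 20%, three categories of operation, and a true difference of 0.

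**1. The plan's own power.** SE = 14 × √(2/50) = 2.80. By the normal approximation, power = Φ(8/2.80 − z).
- One-sided 0.05: Φ(2.857 − 1.645) = 88.7%, close to the stated 90%.
- One-sided 0.025, which corresponds to the lower limit of a two-sided 95% CI: Φ(2.857 − 1.960) = 81.5%.

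The stated power is therefore approximately reproduced only at one-sided 0.05. Section 5 specifies two-sided tests at 0.05 and 95% CIs, so I show both levels.

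**2. Effect of adjusting.** The residual SD becomes 14 × √(1 − R²). Power below is from the noncentral t distribution, with 98 df unadjusted and 96 df with a three-level factor, assuming balanced categories. Half-width = t(0.975) × residual SD × √(2/50).

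| Analysis | Residual SD | SE | Power, one-sided 0.025 | Power, one-sided 0.05 | 95% CI half-width |
|---|---|---|---|---|---|
| Unadjusted | 14.00 | 2.80 | 80.8% | 88.3% | 5.56 |
| Adjusted, R² = 5% | 13.65 | 2.73 | 82.7% | 89.7% | 5.42 |
| Adjusted, R² = 10% | 13.28 | 2.66 | 84.6% | 91.1% | 5.27 |
| Adjusted, R² = 20% | 12.52 | 2.50 | 88.5% | 93.7% | 4.97 |

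At R² = 0 the adjusted power at one-sided 0.025 is 80.74% against 80.76% unadjusted, a cost of about 0.02 percentage points.

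**3. Size of a chance imbalance.** Take two classes of operation, each with 50% prevalence, under simple randomization. The between-arm difference in share has SD √(2 × 0.5 × 0.5/50) = 0.10. If the classes differ by D points on QoR-15, the 95% range of the shift is ±1.96 × 0.10 × D.
- D = 5: ±0.98 points (12% of the margin).
- D = 10: ±1.96 points (24%, 1.96/8 = 0.245).
- D = 15: ±2.94 points (37%).

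At 20% prevalence the SD is √(2 × 0.2 × 0.8/50) = 0.08, and the shifts are ±0.78, ±1.57 and ±2.35 points. The values of D are assumptions. These shifts are already contained in the unadjusted SE of 2.80, so they must not be added to the loss in step 2.

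**The case against.** **Unadjusted analysis is valid.** Under simple randomization, chance imbalance is part of the standard error, so the test keeps its error rate and the CI already allows for such shifts. This stands. A reader might infer an uncorrected bias or an inflated type 1 error; the documents support neither. The wider interval and the possible shift are largely one cost seen twice.

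**The plan is silent, not negative.** A reader might take section 2.1 to rule stratification out. It says only how the list was made and concealed. The supportable statement is that no stratification is described. The analysis uses no stratum in either case.

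**Operation type is not in the data list.** A reader might treat the listed diagnosis as equivalent. It is only a proxy, since one diagnosis can lead to different procedures, so one field has to be added.

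**The gain is assumed and may be small.** At R² = 5% it is 1.9 percentage points of power at one-sided 0.025 (82.7 − 80.8), or 1.4 at one-sided 0.05 (89.7 − 88.3), and 0.14 QoR-15 points of half-width. The SD of 14 may already cover a mixed case load, in which case the sample size already allows for this variation. All of this stands and limits the point to an efficiency gain.

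**A factor does not fit the planned tests.** A t-test, a Mann-Whitney test and a Hodges-Lehmann estimate take no covariate. This is correct, and the fix must name a model. The figures above apply to that normal-theory model only.

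**Broad eligibility suits the aim** of guiding induction choice in elderly day-surgery patients. Agreed; nothing here asks for narrower eligibility.

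**Conclusion.** The point holds as a modest, low-cost gain in precision. For an assumed R² of 5% to 20%, pre-specified adjustment adds about 2 to 8 percentage points of power at one-sided 0.025, or about 1 to 5 at one-sided 0.05, and narrows the 95% CI half-width by 0.14 to 0.59 points (5.56 − 5.42; 5.56 − 4.97). If the operation explains nothing, almost nothing is lost. The size rests wholly on the assumed R², on SD 14 describing the mixed population, and on 50 scored patients per arm.

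A reader might also attribute the gap between 80.8% and the stated 90% to the mix of operations. The documents do not support that: most of the gap comes from the one-sided 0.025 level, since the same unadjusted comparison has 88.3% at one-sided 0.05. Sidedness is a separate matter. The planned comparison is not invalid, and the change is desirable rather than essential.

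**What to change.** 1. Before the list is made, define two or three categories of planned operation. Record the category at screening as a new field.
2. Generate the R list in permuted blocks within category, with one envelope series per category.
3. Make the primary POD 1 QoR-15 analysis, in both FAS and PPS, a linear model with treatment and operation category. Compare the lower limit of the 95% CI for the adjusted mean difference with -8. Keep the Hodges-Lehmann difference as a sensitivity analysis.
4. If recruitment has begun, keep the existing list and add only the factor to the analysis, with the categories fixed and documented before any unblinded outcome data are seen.

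Cost: two or three envelope series, one added data field, 1 to 2 degrees of freedom, and a rewritten primary-analysis paragraph in the statistical section. No extra patients are needed, and eligibility and the margin are unchanged.

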### 2. Research methods

2.1 Study design: Randomized, controlled, parallel non-inferiority trial

Randomization: The randomization result was generated by the investigator using R software, sealed to the envelope and handed over by the patient to the anesthesia nurse before surgery, who was responsible for unpacking the randomized envelope.

Blinding: The anesthesia nurse was responsible for unpacking the randomized envelope and preparing drugs to cover the syringes (with the same appearance and volume), and blinded the anesthesiologist, postoperative visitors and patients.

## 2.2 Sample size estimation:

The primary outcome measure was the quality of postoperative patient recovery (QoR-15 score). According to previous studies, the minimal clinically important difference was 8. The non-inferiority bound for the mean difference between groups was set to -8. Referring to previous studies, the standard deviation (SD) of the QoR-15 scale is 14, and accounting for a 10% shedding rate, 112 achieves 90% of efficacy with a type 1 error of 0.05. We chose to include 112 subjects in this study for the analysis, with 56 subjects in each group.

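### The stated 90% power for 112 patients is not reached after the plan's own 10% loss: about 81% if a two-sided 95% CI is compared with -8, about 88% at one-sided 0.05

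*Combined protocol and SAP*

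**What the plan says.** Section 1.2 (Study Content) describes a "non-inferiority trial to enroll 112 elderly day surgery patients randomized at 1:1". Section 2.2 (Sample size estimation) states that "The non-inferiority bound for the mean difference between groups was set to -8", takes an SD of 14 from earlier studies, and claims that, "accounting for a 10% shedding rate, 112 achieves 90% of efficacy with a type 1 error of 0.05". It then adds: "We chose to include 112 subjects in this study for the analysis, with 56 subjects in each group". Section 4 (Efficacy Evaluation Criteria) fixes the endpoint: "The POD 1 score was the primary study outcome".

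The statistical methods (section 5, part 2) plan t-tests or Mann-Whitney tests according to a normality check. They also report QoR-15 as a Hodges-Lehmann median difference with a 95% CI. On significance they say: "All analyses were assessed using two-sided tests and a P-value less than 0.05 was considered statistically significant".

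No section states the assumed true difference, whether the 0.05 is one- or two-sided for the non-inferiority comparison, or which confidence limit is compared with -8. No 90% CI and no one-sided 0.05 test is planned anywhere.

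**The concern.** A power claim should follow from the margin, SD, level, assumed difference and number of evaluable patients. Here two of these inputs are missing, and the ones that are given do not appear to produce 90%.

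Two things are at stake. The first is the risk of a failed trial. If the two drugs are truly equal, the stated chance of missing non-inferiority is 10%; a lower true power means the sponsor and the ethics committee were given too favourable a figure. The second is the conclusion itself. With the level unstated, the same data could be declared non-inferior against a 90% CI and not against a 95% CI, and that choice would remain open after the data are seen.

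**Working it through.** **Inputs.** Margin 8, SD 14, 10% loss, 112 patients and 56 per arm (section 2.2); 112 is the number enrolled, allocated 1:1 (section 1.2); two-sided 0.05 and 95% CI (section 5, part 2). The true difference is not given; 0 is assumed here and varied below.

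**Evaluable patients.** 112 × 0.9 = 100.8, so about 50 per arm.

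**Standard error of the mean difference.** SE = 14 × √(2/n). With n = 50, SE = 2.80; with n = 56, SE = 2.65.

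**Power, normal approximation.** Power = Φ(8/SE − z). With 50 per arm, 8/2.80 = 2.857:
- one-sided 0.025: Φ(2.857 − 1.960) = Φ(0.897) = 81.5%
- one-sided 0.05: Φ(2.857 − 1.645) = Φ(1.212) = 88.7%

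The noncentral t gives slightly lower values:

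| Evaluable per arm | One-sided 0.025 (t / normal) | One-sided 0.05 (t / normal) |
|---|---|---|
| 50 (after 10% loss) | 80.8% / 81.5% | 88.3% / 88.7% |
| 56 (no loss) | 85.0% / 85.6% | 91.3% / 91.6% |

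**Trying to reproduce the plan's 90%.** Only the bottom right cell exceeds 90%. It needs both one-sided 0.05 and no loss, whereas section 2.2 says the loss is already allowed for.

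**Size needed for 90%.** n per arm = 2 × [14 × (z_α + z_β)/8]², with z_β = 1.282:
- one-sided 0.025: 64.4, so 65 (t: 66); divided by 0.9 and rounded up, 73 (74) per arm, 146 (148) in total
- one-sided 0.05: 52.5, so 53 (t: 54); divided by 0.9 and rounded up, 59 (60) per arm, 118 (120) in total

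**Where 112 may come from.** At one-sided 0.025 and 80% power, the t-based size is exactly 50 per arm. 50/0.9 = 55.6, rounded up to 56, gives 112. The number therefore matches an 80% design at the level implied by a 95% CI. This does not prove its origin.

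**SD that would rescue the claim.** For 50 per arm to give 90%, the SD would have to be about 12.2-12.3 (one-sided 0.025) or 13.6-13.7 (one-sided 0.05), against the stated 14.

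**Sensitivity to the true difference** (50 per arm, normal approximation; positive favours remimazolam):

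| True difference | One-sided 0.025 | One-sided 0.05 |
|---|---|---|
| -1 | 70.5% | 80.4% |
| 0 | 81.5% | 88.7% |
| +0.5 | 85.9% | 91.8% |
| +1 | 89.5% | 94.2% |

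**Effect of the level on the conclusion.** With 50 per arm and SD 14, the CI half-width is 5.56 (95%) or 4.65 (90%). The lower limit exceeds -8 when the observed difference is above -8 + 5.56 = -2.44 or above -8 + 4.65 = -3.35, respectively. An observed difference between -3.35 and -2.44 fails on the first and passes on the second.

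**The case against.** The best defence is that section 2.2 says only 0.05, and non-inferiority is a one-sided question, so one-sided 0.05 is a permissible reading. Power is then 88.3-88.7%, less than 2 points short of 90%, and a small favourable true difference closes the gap: at +0.25, Φ(8.25/2.80 − 1.645) = Φ(1.301), about 90%. If 112 is read as the number analysed, power is 91-92%. It can also be said that the methods section does not establish 0.025. Its two-sided sentence is general, its 95% CI is a Hodges-Lehmann interval offered as an additional summary, and neither is tied to -8.

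Part of this stands. The large shortfall belongs to the 95% CI reading; at one-sided 0.05 it is small. The methods section does not say which limit decides. The power figures are for a mean difference and are not strictly those of the Hodges-Lehmann interval.

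It does not save the claim. One-sided 0.05 still falls short once the stated loss is applied, and it conflicts with the only level and interval the methods section gives. Reading 112 as the number analysed contradicts section 1.2 and the loss allowance in section 2.2. No favourable difference is stated, and an unfavourable one lowers power just as readily. Section 2.2 sets the margin on the mean difference, so the mean-difference calculation is the relevant one.

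**Conclusion.** The concern holds. With margin 8, SD 14, a true difference of 0 and about 50 evaluable patients per arm, 112 enrolled patients do not give 90% power on either level. If the drugs are equal, the chance of missing non-inferiority is about 19% with the 95% CI and about 12% at one-sided 0.05, rather than 10%.

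The arithmetic is certain given these inputs. Which of the two figures applies depends on a decision rule the plan does not state; the 95% CI reading fits the methods section better. The trial remains viable at about 81%, so this should be fixed but does not invalidate the design.

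**What to change.** In section 5, part 2, add a rule such as: *Non-inferiority is concluded if the lower limit of the two-sided 95% CI for the mean difference in POD 1 QoR-15 (remimazolam minus etomidate) is above -8 (one-sided 0.025).* Mark the Hodges-Lehmann interval as supplementary, so that one effect measure decides.

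In section 2.2, state the same rule and replace the power claim with: *112 patients (56 per group) will be randomised. With 10% loss, about 50 per group are evaluable; with SD 14, true difference 0 and margin -8, power is about 81% at one-sided 0.025.* Remove the words that present 112 as the number analysed.

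This costs wording in two sections and no extra patients; the stated power becomes less favourable. If the sponsor wants to keep 90% under this rule, 146-148 patients would have to be randomised. If a different level or a non-zero true difference was intended, it should be stated and justified in both sections, with the power that follows from it. Whichever rule is chosen should be fixed before outcome data are examined.
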